13.3.3 VITAL SIGN MEASUREMENTS

Descriptive statistics (mean, median, standard deviation, minimum, and maximum) of the actual values and the change from baseline in vital sign measurements, including weight, will be presented by visit.

A table summarizing clinically notable blood pressure and weight measurements which are aligned with CTCAE cut-offs, where available, will be displayed. The proportion of subjects whose worst observed values while on study treatment (on or after the first day of treatment) meet the following clinically notable criteria will be tabulated by treatment arm:

- Systolic Blood Pressure
 - < 85 mm Hg
 - $\geq 140 - < 160$ mm Hg
 - ≥ 160 mm Hg

- Diastolic Blood Pressure
 - < 50 mm Hg
 - ≥ 90 - < 100 mm Hg
 - ≥ 100 mm Hg
- Weight gain from baseline
 - $\geq 5\%$ - < 10% increase
 - $\geq 10\%$ - < 20% increase
 - $\geq 20\%$ increase
- Weight loss from baseline
 - $\geq 5\%$ - < 10% decrease
 - $\geq 10\%$ - < 20% decrease
 - $\geq 20\%$ decrease

The derived visit window definitions for vital signs are displayed in Table 6.

Table 6. Analysis Window Definitions for Vital Signs Results

Visit	Nominal Day	Range
Baseline	1 (first dose date)	[-14, 1]
Week 4	28	[2, 55]
Week 12	84	[56, 111]
Week 24	168	[112, 195]
Week 36	252	[196, 279]
Week 48	336	[280, 363]
⋮	⋮	⋮
Week XX	XX times 7	[(Week XX-1 upper range + 1, (XX times 7) + 27]
EOT	Last dose date	[Last dose date, Last dose date + 15]
30 days post EOT	Last dose date + 30 days	[Last dose date + 16,]

13.3.4 PHYSICAL EXAMINATIONS

Physical examination information will be provided in a subject listing and include at minimum: subject id, treatment arm, visit, assessment date, physical examination, results and clinical findings (if applicable).

13.3.5 SUPPLEMENTAL PROCEDURES

Procedures received from the first day of treatment to the last day of treatment will be summarized by SOC class and preferred term.

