6.5 Pacritinib Treatment Adjustments for Adverse Events

6.5.1 Treatment Interruption and Discontinuation

Safety parameters including AEs, hematology, cardiac monitoring, and serum chemistry will be assessed according to the protocol. Pacritinib treatment may be withheld for up to 7 days due to drug-related toxicities. A longer recovery period may be allowed based on the toxicity, but must be agreed upon between the investigator and medical monitor.

Pacritinib should be withheld 7 days prior to planned invasive procedures and concurrently with any unplanned invasive procedure. Pacritinib may be restarted after 2 days without active signs or symptoms of active bleeding.

After treatment interruption, patients may resume pacritinib treatment per dose management guidelines below.

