		 If grade 4 thrombocytopenia recurs after restarting drug, pacritinib must be discontinued.
Hemorrhage	 Treatment-emergent grade 2 hemorrhage 	 Hold pacritinib for up to 7 days until hemorrhage resolves. Restart pacritinib at the same dose.
		• If event recurs, hold until resolution then restart at the next lower dose. If at 100 mg QD dose level, discontinue.
	■ grade 3	 Hold pacritinib for up to 7 days and start at the next lowest dose level once resolved. If at 100 mg QD dose level, discontinue.
	■ grade 4	Discontinue pacritinib
Febrile neutropenia	■ grade 4	 Hold pacritinib for up to 7 days and start at the next lowest dose level once resolved. If at 100 mg QD dose level, discontinue.
Neutropenic infections, including neutropenic sepsis	■ grade 4	 Hold pacritinib for up to 7 days and start at the next lowest dose level once resolved. If at 100 mg QD dose level, discontinue.

Table 3.	Treatment 7	Foxicity and	I Dosage	Management:	Hematologic	Toxicities and Related	Complications
----------	-------------	---------------------	----------	-------------	-------------	-------------------------------	---------------

Coagulation Testing

Coagulation testing will include PT, INR, PTT, and TT at screening, baseline, the end of Week 4, the end of Week 12, the end of Week 24, or the end of treatment visit, and 30 days after the last dose of study treatment. Additional coagulation testing should be done as clinically indicated.

These results will be taken into account, together with baseline platelet counts and prior medical history of bleeding, to help guide ongoing hematologic monitoring of platelet counts and clinical monitoring for bleeding. Pacritinib dosage modifications will be implemented for clinically significant AEs identified with this testing per the guidelines in Table 7.

6.5.3 Pacritinib Dosage Management Guidelines for QTc Interval Prolongation, Reduction in Ejection Fraction, and Other Cardiac Toxicities

A 12-lead ECG (collected in triplicate) will be checked at screening, baseline, the end of Week 4, the end of Week 12, the end of Week 24 or the end of treatment visit, including QTc calculation, and 30 days after the last dose of study treatment.

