Abbreviations: CTCAE = Common Terminology Criteria for Adverse Events; LVEF = left ventricular ejection fraction

In patients who resume pacritinib treatment after holding treatment for grade 2 QTc interval prolongation, follow-up ECGs (in triplicate) are recommended on Days 1, 7, 14, 28, and 56 after pacritinib restart. After restart of pacritinib, QTc monitoring should follow this schedule with ECGs obtained in triplicate:

- Restart Day 1 at 4 hours (± 1 hour) after ingestion of the first reduced dosage
- Restart Day 7 (\pm 2 days) 4 hours after dosing (\pm 1 hour)
- Restart Day 14 (± 2 days) 4 hours after dosing (± 1 hour)
- Restart Day 28 (± 2 days) at any time relative to dosing
- Restart Day 56 (± 7 days) at any time relative to dosing

If grade 2 toxicity does not resolve to grade ≤ 1 within 7 days, discontinue all treatment with pacritinib. If grade 2 toxicity recurs despite dosage reduction discontinue all treatment with pacritinib. For grade 3 and 4 QTc prolongation, discontinue all treatment with pacritinib.

Other Cardiac Toxicities

Discontinue treatment with pacritinib for all other grade 3 and 4 cardiac toxicities.

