8.3 PRIOR THERAPY AND CONCOMITANT MEDICATIONS

Prior therapy is any therapy or medication taken prior to informed consent. Prior therapy includes both prior MF and non-MF therapies. Both will be summarized for all enrolled patients by treatment and overall.

A medication will be considered a concomitant medication if it was taken by the patient at any time on study (on or after the first day of treatment and within 30 days after the last dose of study drug). The following will also be considered concomitant medications:

- Medications missing both start and stop dates.
- Medications having a start date prior to the last dose of study drug and missing the stop date.

Concomitant medications will be summarized by ATC class and preferred term in each treatment arm. Prior MF and non-MF therapies or medications will be summarized by Anatomic Therapeutic Chemical (ATC) class and preferred term using WHO Drug Dictionary version 01, March 2013.

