9. EXPOSURE TO STUDY TREATMENT

Exposure to study treatment will be evaluated by the duration of treatment, cumulative dose, actual dose intensity, and relative dose intensity in the safety population.

Duration of treatment (weeks): is defined as the duration from first day of study treatment to the last day of study treatment, i.e.,

$$\frac{(\text{Date of last dose of study treatment} - \text{date of first dose of study treatment} + 1)}{7}$$

Descriptive statistics will be provided for duration of treatment by treatment arm.

Cumulative dose (mg): is defined as the sum of all doses of study treatment taken and descriptive statistics will be provided by treatment arm. The counts and percentages of patients with any dose modifications will be provided by treatment arm. Reasons for dose modifications will also be summarized.

Actual dose intensity (ADI, mg/day) = (total dose taken in mg) ÷ (duration of treatment in days) and descriptive statistics will be provided by treatment arm.

Relative dose intensity (RDI, %) = (ADI) ÷ (planned daily dose) * 100. The planned pacritinib dose is 100, 200, and 400 mg/day in the pacritinib 100 mg QD, 100 mg BID, and 200 mg BID arms, respectively. Descriptive statistics will be provided by treatment arm.

Study drug modification categories will be defined for drug holds and drug reduction. Drug holds will be identified by those records with dose entered as 0mg. Drug reduced will be identified by evaluating the subject's initial dose and determining if a reduction occurred at any time during the treatment period.

Finally, reasons for drug modifications will be presented by treatment arm.

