13 SAFETY ANALYSES

Safety analyses include summaries and graphical presentations of treatment emergent adverse events, clinical labs, ECG, vital signs, performance status, and any abnormal findings observed during the performance of physical examinations by treatment received after randomization through the end of assigned study treatment + 30 days.

The primary safety measure for dosage selection is the percentage of patients with CTCAE grade 3/4 cardiac treatment-emergent AEs, CTCAE grade 3/4, hemorrhage treatment-emergent AEs, CTCAE grade ≥ 4 thrombocytopenia toxicity, or CTCAE grade ≥ 4 anemia toxicity. Cardiac and hemorrhage treatment-emergent AEs will be determined using Standardized MedDRA Query (SMQ). See section 9.1 for more details. Thrombocytopenia and anemia will be determined by central laboratory measurement.

All other safety data including TEAEs, death, and clinical laboratory measures will be used as supportive measures for evaluation of pacritinib dose-safety relationship.

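### The procedures table closes at the last dose while adverse events and concomitant medications run 30 days longer, so procedures done after the final dose for a treatment-ending toxicity are left out

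*SAP*

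**What the plan says.** SAP 13.3.5 is a single sentence: "Procedures received from the first day of treatment to the last day of treatment will be summarized by SOC class and preferred term". It has no post-treatment days, does not define the last day of treatment, and does not mention treatment arm. The nearest definition is in SAP 9, where treatment duration "is defined as the duration from first day of study treatment to the last day of study treatment" and the formula uses the date of the last dose.

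Other parts of the SAP run longer. A concomitant medication is one taken "on or after the first day of treatment and within 30 days after the last dose of study drug" (SAP 8.3). Adverse events are treatment-emergent up to 30 days after the last study treatment date (SAP 11.1). On-treatment deaths include those within 30 days of discontinuation (SAP 13.1). The opening of SAP 13 describes safety summaries "by treatment received after randomization through the end of assigned study treatment + 30 days"; its list of data types does not name procedures.

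On the protocol side, section 6.5.1 says: "Pacritinib should be withheld 7 days prior to planned invasive procedures and concurrently with any unplanned invasive procedure", followed by "Pacritinib may be restarted after 2 days without active signs or symptoms of active bleeding". For grade 4 hemorrhage, Table 3 says: "Discontinue pacritinib". Table 4 stops treatment at grades 3 and 4 for QTc prolongation, reduced ejection fraction and other cardiac toxicity, and section 6.5.3 adds: "Discontinue treatment with pacritinib for all other grade 3 and 4 cardiac toxicities". Table 5 makes an exception: a patient who entered with a grade 2 ejection fraction and falls to grade 3 is held and reassessed, and may resume.

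**The concern.** Under the SAP 13.3.5 window, whether a procedure is counted depends on what happened to the patient afterwards. If dosing resumes at any later date, a procedure done during the interruption lies before the last dose and is in. If dosing never resumes, the same procedure on the same calendar day lies after the last dose and is out. The protocol ends treatment for the most severe bleeding and cardiac events, so the procedures lost tend to be those done for such events.

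At stake is the consistency of the safety report. A reader tracing a grade 4 bleed would find the event and its drug treatment in the tables but might not find the endoscopy, surgery or other intervention done for it, and nothing in the table would show that it had been cut off by date. Bleeding and cardiac events are the toxicities on which the study's safety review is centered, so this is the wrong place for an unexplained gap, even in a secondary table.

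**Working it through.** There is no stated figure to reproduce, because the point concerns a date window. The check sets the windows side by side and then asks whether the documents allow the loss to be sized.

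**Step 1: the date rule.** Let L be the study day of the last dose and d the day of the procedure. Reading the last day of treatment as the last dose date, as SAP 9 does:

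- SAP 13.3.5 counts the procedure if 1 ≤ d ≤ L.
- A window matched to concomitant medications would count it if 1 ≤ d ≤ L + 30.

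| Day relative to last dose (d − L) | SAP 13.3.5 | 30-day window |
|---|---|---|
| −3 | in | in |
| 0 | in | in |
| +1 | out | in |
| +7 | out | in |
| +30 | out | in |
| +31 | out | out |

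The two rules differ only on days L + 1 to L + 30.

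**Step 2: which procedures fall on those days.**

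- *Planned invasive procedure, dosing resumes.* The hold starts about 7 days before, but a later dose moves L past the procedure. Counted.
- *Planned invasive procedure, dosing never resumes.* L is about 7 days before the procedure, so d is about L + 7. Not counted.
- *Unplanned procedure, a dose already taken that day.* d is no later than L. Counted.
- *Unplanned procedure after the final dose day, no restart.* d ≥ L + 1. Not counted.
- *Procedure for a grade 4 hemorrhage or discontinuing cardiac toxicity.* Counted if on the last-dose day or earlier, otherwise not.

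**Step 3: can the loss be sized?** The quantity needed is the proportion of patients who have a procedure on days L + 1 to L + 30. The documents give no procedure rate. The nearest figures are pooled phase 3 cardiac rates at 200 mg BID (Protocol 1.3.4, Cardiac Toxicities): 3.8% with a grade 3/4 event and 0.9% with a cardiac event leading to discontinuation. Protocol 11.7 plans up to 50 patients per arm.

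The chance of at least one event among n patients is 1 − (1 − p)^n. As a check on the formula, p = 5% and n = 50 give 1 − 0.95^50 = 92.3%, which matches the 92% in Protocol 11.7. Assuming the earlier rates carry over:

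- p = 3.8%: expected 50 × 0.038 = 1.9 patients; chance of at least one 1 − 0.962^50 = 86%.
- p = 0.9%: expected 50 × 0.009 = 0.45 patients; chance of at least one 1 − 0.991^50 = 36%.

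These are patients with a cardiac event, not patients with a procedure, and hemorrhage is not included. They show that treatment-ending cardiac events may plausibly occur in an arm of this size. They do not estimate the number of procedures lost.

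**The case against.** The strongest reply is that little depends on this table. Dosage selection rests on grade 3/4 cardiac and hemorrhage events and on grade 4 or higher laboratory thrombocytopenia and anemia (SAP 13). Serious events, events leading to discontinuation, fatal events, and onset and resolution of cardiac and hemorrhage events are reported separately (SAP 13.1). A bleed that ends treatment is fully counted there. Splenectomy, other splenic surgery and splenic irradiation are also in the SAP 13.3.6 listing, with no cut-off at the end of treatment. All of this stands and sets the size of the point.

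Second, SAP 13.3.1 and 13.3.2 also stop ECG and ejection fraction summaries at the last dose, so an on-treatment window is not unique to procedures. That is true. Those are largely scheduled measurements, however, whereas procedures are often responses to events and are closer in kind to concomitant medications. The heading of SAP 17.5 itself pairs the two for date handling, yet their cut-offs differ with no reason given.

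A reader might also infer that the protocol's invasive-procedure rule pushes such procedures out of the table generally. The documents do not support that. The rule is a hold with restart allowed, and it leads to exclusion only when dosing never resumes.

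Finally, collection is uncertain. The assessments calendar (Protocol Table 1) has adverse events and concomitant medications at the 30-day post-treatment visit but no procedures row, and transfusion history is not marked there. Protocol 9.1.2 does ask for treatment given for an adverse event to be captured on the case report form. This limits how complete a longer table would be; it is not a reason to discard what is recorded.

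**Conclusion.** The mismatch is real and small. As written, SAP 13.3.5 omits procedures done after the final dose, including those for toxicities that ended treatment, while the related events and medications are counted for 30 more days. The omission depends on outcome, since it turns on whether the patient resumed dosing, and it is confined to one descriptive table in a study with no formal hypothesis test.

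The conclusion rests on two readings: that the last day of treatment means the last dose date, and that the opening sentence of SAP 13 does not override the narrower wording of 13.3.5.

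Two stronger readings are tempting and should not be drawn. One is that the burden of serious toxicity is understated for dose selection, most of all in the arm with most treatment stops. The events themselves are counted to 30 days in the primary safety measure and adverse event tables, and nothing in the documents shows how lost procedures would divide between arms. The other is a count of about 2 to 4 lost per 50 patients, from the grade 3/4 cardiac rates of 3.8% and 8.6% (50 × 0.038 = 1.9; 50 × 0.086 = 4.3). Those rates count events rather than procedures, and the 8.6% comes from 400 mg QD, which is not an arm of this trial. The number lost cannot be computed from the documents.

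**What to change.** Reword SAP 13.3.5 so that procedures are summarized from the first dose date through 30 days after the last dose of study treatment, by treatment arm, with a flag for those performed after the last dose. The flag lets a reader recover the on-treatment table. If the sponsor prefers the shorter window, SAP 13.3.5 should say why it differs from concomitant medications.

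The cost is one phrase of text, one date condition and one flag; no clinical rule changes. The downside is that post-dose procedures may be less completely recorded, because the calendar has no separate procedures row at the 30-day visit, and patients who move to expanded access do not have that visit. A table footnote should say so.

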13.3.6 PROGRESSIVE DISEASE

Progressive disease information will be presented in a subject listing and include at minimum: subject id, age, treatment arm, assessment date, splenic progression status, progression date, form of splenic progression (increase in splenic volume of $\geq 25\%$ from baseline, splenectomy or other splenic surgery, splenic irradiation), leukemic transformation status, transformation date, form of leukemic transformation (peripheral blood blast $\geq 20\%$ sustained for 8 weeks, bone marrow blast $\geq 20\%$) and treatment end date.

13.3.7 SUBGROUP ANALYSIS OF SAFETY

If there are enough patients per group, treatment-emergent adverse events, including all AEs, grade 3/4 AEs, and SAEs, and hematology toxicity may also be summarized by subgroups as appropriate. Subgroups may include, but are not limited to, baseline platelet count ($\leq 50,000/\mu\text{L}$ vs. $> 50,000/\mu\text{L}$) and baseline hemoglobin ($< 100 \text{ g/L}$ vs. $\geq 100 \text{ g/L}$).

14 GENETIC BACKGROUND

Details of the genetic background analysis can be found in the DNA analysis plan.

15 PHARMACOKINETIC AND PHARMACODYNAMIC ANALYSES

Details of the PK/PD analysis can be found in the PK/PD analysis plan.

16 DETERMINATION OF SAMPLE SIZE

The determination of sample size for this dosage finding study was driven by a targeted predictive probability (see Table 3) and to ensure adequate precision to evaluate efficacy using percent reduction of spleen volume from baseline. Based on past clinical experience (e.g., $\leq 10\%$ SVR

deemed as the minimally, clinically meaningful reduction), variance in percent reduction in spleen volume (standard deviation $\approx 20\%$) from PERSIST-1 and PERSIST-2 studies, and the need for exploratory modeling analysis of pacritinib dose-response and dose-exposure-response relationship, a maximum of 30 evaluable patients per treatment arm are adequate to evaluate efficacy.

As for safety, with a sample size of 30 patients per arm, if the true incidence rate for a specified safety event is 5% among patients per each arm, then the chance of observing at least 1 event among 30 patients will be 78%. At the end of the study, if none of the 30 patients in each treatment arm experience an AE, then the true incidence rate of the AE is no greater than 5.2% with 80% confidence and no greater than 7.4% with 90% confidence.

A 15% overage will be built into the study sample size to account for potential drop-outs, thus a maximum of 35 patients are planned for enrollment per treatment arm.

17 DATA HANDLING RULES

17.1 Definition of Baseline Value

The baseline value for safety analyses will be defined as the last assessment prior to the start of treatment, unless otherwise specified.

17.2 Partial Current MF Diagnosis Date

For patients who have a partial diagnosis date, the 15th of the month will be used if day is missing, and July 15th will be used if both the month and day are missing.

17.3 Partial or Missing AE Onset and Resolution Dates

For AE summaries, the missing day of onset of an adverse event will conservatively be set to:

- First day of the month that the AE occurred if this is after the date of the start of first treatment.
- One day after the first treatment if this is the same month that the AE occurred.
- The 15th of the month and year if the AE month and year are before the month and year of the first treatment.

If the onset date of an adverse event is missing both day and month, it will be set to:

- January 1 of the year of onset, as long as this is after the first study treatment.
- One day after the first study treatment if this is the same year that the AE occurred.
- July 1st of the year if the AE year is before the year of the first study treatment.

If the day of resolution of an adverse event is missing, it will conservatively be set to the last day of the month or 30 days after the last dose of study treatment if this day is in the same month and year,

whichever is earlier. If the day of resolution of an adverse event is missing both day and month, it will conservatively be set to the last day of the year or 30 days after the last dose of study treatment if this day is in the same year, whichever is earlier.

All missing and partial dates will be presented “as is” in listings.

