11 SAFETY VARIABLES

11.1 ADVERSE EVENTS

An adverse event (AE) is any untoward medical occurrence in a patient or clinical investigation subject administered a pharmaceutical product and which does not necessarily have to have a causal relationship with this treatment. All AEs, including serious adverse events (SAEs) will be collected during the clinical study from the time the patient signs the informed consent through 30 days following the last dose of study treatment. For screened patients who are not randomized, only

SAEs occurring between the time of informed consent and determination of screen failure are to be reported.

A TEAE is defined as an adverse event (AE) occurring after the first dose of study treatment and within 30 days after the last study treatment date. In addition, an AE with a missing start date but with an end date after the first study drug dose date is also considered a TEAE. An AE occurring after the first dose of study drug that also occurred prior to the first dose of study drug is only considered a TEAE if the AE worsened in grade after the first dose of study drug.

Analysis of AEs will be based on Treatment Emergent Adverse Events (TEAEs).

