17.4 Partial or Missing Transfusion Dates

For transfusion summaries, the missing day of transfusion start date will conservatively be set to:

- First day of the month that the transfusion occurred if this is after the date of the start of first treatment.
- One day after the first treatment if this is the same month that the transfusion occurred.
- The 15th of the month and year if the transfusion month and year are before the month and year of the first treatment.

If the onset date of the transfusion is missing both day and month, it will be set to:

- January 1 of the year of onset, as long as this is after the first study treatment.
- One day after the first study treatment if this is the same year that the transfusion occurred.
- July 1st of the year if the transfusion year is before the year of the first study treatment.

If the day of resolution of transfusion is missing, it will conservatively be set to the last day of the month or 30 days after the last dose of study treatment if this day is in the same month and year, whichever is earlier. If the day of resolution of transfusion is missing both day and month, it will conservatively be set to the last day of the year or 30 days after the last dose of study treatment if this day is in the same year, whichever is earlier.

All missing and partial dates will be presented “as is” in listings.

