17.5 Partial or Missing Concomitant Medication and Supplemental Procedure Dates

For concomitant medication, when missing the start date information the following imputation will be applied:

Derive data only with the missing day of the month:

- First day of the month that the CM occurred if this is after the date of the start of first treatment.
- One day after the first treatment if this is the same month that the CM occurred.
- The 15th of the month and year if the CM month and year are before the month and year of the first treatment.

Derive data if both day and month are missing:

- January 1 of the year of onset, as long as this is after the first study treatment.
- One day after the first study treatment if this is the same year that the AE occurred.
- July 15th of the year if the CM year is before the year of the first study treatment.

When missing the end date information the following imputation will be applied:

Derive data only with the missing day of the month:

- Set as the last day of the month

Derive data with both missing day and month:

- set as December 31th

All missing and partial dates will be presented “as is” in listings

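### SAP 17.3 and 17.5 impute a partial start date to the day after first dose without checking a known end date, so an AE that resolved before treatment is counted as treatment-emergent

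*SAP*

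**What the plan says.** - **AE onset, day missing (SAP 17.3).** The imputed date is "One day after the first treatment if this is the same month that the AE occurred". If day and month are both missing, the same date is used when the year of onset is the year of first dose. The section describes the missing-day setting as conservative.
- **Medication start (SAP 17.5).** The template is repeated: "One day after the first treatment if this is the same month that the CM occurred" for a missing day, and "One day after the first study treatment if this is the same year that the AE occurred" when the month is missing too. The second line still refers to an AE although the section concerns medications.
- **Transfusion start (SAP 17.4).** Again the same: "One day after the first treatment if this is the same month that the transfusion occurred".
- **Treatment-emergent definition (SAP 11.1).** A TEAE is an event "occurring after the first dose of study treatment and within 30 days after the last study treatment date". Two further clauses follow. One adds events: "an AE with a missing start date but with an end date after the first study drug dose date is also considered a TEAE". The other concerns events also present before first dose; such an event "is only considered a TEAE if the AE worsened in grade after the first dose of study drug".
- **Concomitant definition (SAP 8.3).** A drug is concomitant if taken on or after the first treatment day and up to 30 days after the last dose. The section does not say how an imputed start is weighed against a recorded stop.

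None of the three imputation sections makes the imputed start depend on a recorded end date. All three state that partial dates appear unaltered in listings.

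**The concern.** AEs are collected from informed consent, and the screening procedures in Protocol Table 1 run from Day -35 to Day -7. An AE can therefore begin and end before first dose and still share a month, or a year, with it. If its onset is only partly known, SAP 17.3 moves it to the day after first dose even when the resolution date shows that it was already over.

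Moving onset towards the treatment period is sensible when the timing is unknown. Here the end date settles the timing, and the rule overrides it. At stake are a few pre-treatment events in the TEAE summaries of a study whose purpose is to weigh safety between doses, and medication records with a start later than their stop.

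**Working it through.** The plan states no figure on this point, so there is none to reproduce. The check applies the rules as written to illustrative records.

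**Inputs.** Imputation rules from SAP 17.3 and 17.5; TEAE window from SAP 11.1. The dates are assumptions chosen to show the mechanism.

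**Formulas.**
- Imputed start = first dose + 1 day, if the month matches (day missing) or the year matches (day and month missing).
- TEAE if first dose < onset ≤ last dose + 30 days.
- Implied duration = end − start + 1 day.

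| Record | First dose | Start as recorded | Known end | Imputed start | Implied duration (days) |
|---|---|---|---|---|---|
| AE | 20 May | May | 12 May | 21 May | −9 + 1 = −8 |
| AE | 20 Mar 2018 | Mar 2018 | 10 Mar 2018 | 21 Mar 2018 | −11 + 1 = −10 |
| AE | 20 Mar 2018 | 2018 | 10 Feb 2018 | 21 Mar 2018 | −39 + 1 = −38 |
| Drug | 20 Mar 2018 | Mar 2018 | 10 Mar 2018 | 21 Mar 2018 | −11 + 1 = −10 |
| Drug | 20 Mar 2018 | 2018 | 31 Jan 2018 | 21 Mar 2018 | −49 + 1 = −48 |

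**Adverse events.** Each AE ended before first dose, yet its imputed onset lies in the TEAE window. Neither extra clause of SAP 11.1 rescues it:
1. The end-date clause only adds events with a missing start that end after first dose. It excludes nothing.
2. The worsening clause needs an occurrence dated before first dose. The imputation has removed that date.

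The plan is also uneven. The end-date clause does not make a TEAE of an AE with a wholly missing onset that ended before first dose. An AE with the same end date and a known onset month or year becomes one. More information gives the worse answer.

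**Medications.** SAP 17.5 forces the start after the stop in both drug rows. If the program tests only the imputed start against the on-study window, the drug is concomitant. If it also requires the stop to be on or after first dose, it is not. SAP 8.3 does not settle which.

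**Where the rule bites.** Take every first-dose date in 2018 and every episode that starts and ends within Days -35 to -1, all weighted equally. The rule turns about 25% of these episodes into TEAEs with onset after their end when only the day is missing, and about 94% when day and month are missing. These are shares of hypothetical partial-date records with a known pre-treatment end. They are not rates for this study.

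**After the fix.** With the imputed start capped at the known end, the three AEs are pre-treatment, the two drugs are not concomitant, and no start follows its end.

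**The case against.** The strongest case against is that the rule is deliberately conservative, touches only partial dates, and has little reach. Onset and resolution dates are to be captured for every AE (Protocol 9.1.2) and incomplete data are queried (Protocol 10.2). No hypothesis test depends on the result. All of this stands, and it limits the size of the point. It does not answer the record whose end date is known, because there nothing is left to be conservative about.

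A reader might infer more than the documents support:
- **That every matching month or year triggers the rule.** It applies only to partial dates, and the year match only when day and month are both missing.
- **That the AE listings will show negative durations.** SAP 17.3 limits imputation to summaries and keeps partial dates unaltered in listings. The times to onset and resolution that SAP 13.1 also wants graphed could be affected only if they are derived from imputed dates, which the SAP does not say.
- **That stopped ruxolitinib or hydroxyurea will appear as prohibited therapy.** A drug with a known stop before Day 1 does not meet SAP 8.3's definition on its plain sense. Protocol 6.6 permits up to two weeks of hydroxyurea in the first month, and prior ruxolitinib has its own summary in SAP 8.4.
- **That baseline transfusion frequency is distorted generally.** The formulas in SAP 10.6.1 and 10.6.2 add Transfusion History counts by source. Only a partly dated transfusion between consent and first dose could move, and without a known end date its true timing is unknown.
- **That the primary safety measure is compromised.** Two of its four components rest on central laboratory values. The other two need cardiac or hemorrhage events of grade 3 or higher, and the recent bleeding and cardiac exclusions in Protocol 4.1.2 would usually bar a patient with such an event during screening. An effect is remote.

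**Conclusion.** The point holds in a narrow form. Read together, SAP 17.3 and 11.1 count an AE known to have resolved before first dose as treatment-emergent, with an onset after its own resolution. SAP 17.5 likewise produces a medication start after a known stop; the concomitant label does not follow with certainty, because it depends on how SAP 8.3 is programmed. This is a stated rule giving a wrong result, not an omission.

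The size is minor. It is limited to partial-date records in the month of first dose (or the year, if the month is also missing) whose known end date precedes first dose. The documents give no count, and the number is probably small. The conclusion assumes that the rules are programmed as written, with no unstated end-date check.

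**What to change.** Add to SAP 17.3 and 17.5, and to 17.4 where an end date is recorded:
1. An imputed start may not be later than a known end date.
2. A record whose known end date is before first dose is classed as pre-treatment, or as prior therapy where SAP 8.3's definition is met. It does not enter the TEAE or concomitant summaries.

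Keep the existing rule of first dose plus one day wherever the end date is missing, or too incomplete to settle the timing. At the same time, correct the stray reference to an AE in the year-match line of 17.5.

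The cost is one sentence per subsection and one programming check that flags any imputed start later than its end. No data collection or design feature changes.
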